3. INTRODUCTION

Gepotidacin (GSK2140944) is a novel, bactericidal, first-in-class triazaacenaphthylene antibiotic that inhibits bacterial DNA replication by a distinct mechanism of action [Gibson, 2019; Bax, 2010] and equally and independently binds to 2 different type II topoisomerase enzymes [Oviatt, 2022].

This provides activity against most strains of *Escherichia coli* and *Staphylococcus saprophyticus*, including isolates resistant to current antibiotics [Biedenbach, 2016; Mushtaq, 2019]. Due to the equal and independent binding at both enzymes, mutations in both enzymes are needed to significantly affect gepotidacin susceptibility [Oviatt, 2022].

Gepotidacin has been evaluated in Phase II studies for the treatment of ABSSSIs, uncomplicated urogenital gonorrhea, and uncomplicated UTI. Phase III studies are ongoing to evaluate oral gepotidacin for the treatment of uncomplicated urogenital gonorrhea and uncomplicated UTI (acute cystitis).

Gepotidacin selectively inhibits bacterial DNA replication by interacting in a unique way on the GyrA subunit of bacterial DNA gyrase and the ParC subunit of bacterial topoisomerase IV. This interaction appears to be highly specific to bacterial topoisomerases as evidenced by weak in vitro inhibition of human topoisomerase II α , supporting the selective activity of gepotidacin against the bacterial target. The novel mode of action of this new class antibacterial affords in vitro activity against most target pathogens resistant to established antibacterials, including fluoroquinolones.

3.1. Study Rationale

This study is being conducted based on the need to identify new and effective antibiotic treatment options for gonorrhea as antimicrobial resistance continues to rise worldwide (see Section 3.2) and based on the results of an open-label, dose-ranging Phase II study of gepotidacin for the treatment of adults with uncomplicated urogenital gonorrhea caused by NG.

Study BTZ116576 was a Phase II, randomized, multicenter, open-label, dose-ranging study evaluating the efficacy, safety, and tolerability of gepotidacin therapy in adult participants with uncomplicated urogenital gonorrhea caused by NG. Participants were administered single oral doses (1500 or 3000 mg) of gepotidacin on Day 1 with a Test-of-Cure (TOC) (Day 4 to 8) Visit. A total of 69 participants (1500 mg: 30 participants; 3000 mg: 39 participants) were included in the Microbiologically Evaluable Population. The primary aim of the study was to provide evidence for 95% bacterial eradication of urogenital NG in the Microbiologically Evaluable Population at the TOC Visit (cure rate) and to exclude the null hypothesis that the cure rate was 80% or less. Microbiological success was achieved by 97% and 95% of participants (lower 1-sided exact 95% confidence interval [CI] bound, 85.1% and 84.7%, respectively) in the 1500- and 3000-mg treatment groups, respectively. Microbiological success (bacterial eradication) was also evaluated for pharyngeal and rectal NG, with 1 of the 2 participants with pharyngeal NG and all 3 participants with rectal NG achieving microbiological success. In Study BTZ116576, gepotidacin was active in vitro

against the 69 baseline urogenital NG isolates recovered, with a gepotidacin minimum inhibitory concentration (MIC) range of ≤ 0.06 to $1 \mu\text{g/mL}$ and 50th and 90th percentile minimum inhibitory concentration (MIC_{50} and MIC_{90}) values of 0.12 and $0.5 \mu\text{g/mL}$, respectively. Additional study results demonstrated that some baseline urogenital NG isolates were resistant to ciprofloxacin, penicillin, and/or tetracycline.

This Phase III study (BTZ116577) aims to evaluate oral gepotidacin compared to intramuscular (IM) ceftriaxone plus oral azithromycin, a currently recommended treatment regimen, for the treatment of uncomplicated urogenital infection caused by NG in adolescent and adult participants.

3.2. Background

Gonorrhea is the second most prevalent bacterial sexually transmitted infection globally and remains an important clinical and public health problem throughout the world. In 2012, an estimated 78 million cases of gonorrhea occurred among 15- to 49-year-olds worldwide with a global incidence rate of 19 per 1000 females and 24 per 1000 males [WHO, 2016]. Gonococcal infections following sexual and perinatal transmission are a major source of morbidity worldwide [Barry, 2009]. Infections can involve cervicitis, proctitis, urethritis, pelvic inflammatory disease, and pharyngitis. Complications include infertility, ectopic pregnancy, chronic pelvic pain, adverse outcomes of pregnancy, disseminated gonococcal infection, and increased susceptibility to and transmission of human immunodeficiency virus [Workowski, 2008; Barry, 2009].

A variety of antimicrobial agents have been used over the years for the treatment of gonorrhea; however, effective treatment options for gonorrhea have diminished rapidly because of the emergence and worldwide spread of antimicrobial resistance to many drugs previously used or considered first line, i.e., penicillins, narrow-spectrum cephalosporins, tetracyclines, macrolides, and fluoroquinolones [Workowski, 2008; Barry, 2009]. At the start of the present study, the recommended treatment for urogenital gonorrhea per the European Union, United States (Centers for Disease Control and Prevention [CDC]), and World Health Organization (WHO) guidelines is an IM injection of ceftriaxone combined with a single oral dose of azithromycin [Bignell, 2013; CDC, 2015; WHO, 2016]. As of Dec 2020, the CDC now recommends an IM injection of ceftriaxone based on body weight and an oral regimen of doxycycline if chlamydia infection has not been ruled out [CDC, 2021]. While these guidelines may help delay the emergence of cephalosporin-resistant gonorrhea by using combination antibacterial therapy, they are not able to eliminate this impending threat. Therefore, drug-resistant NG has been labeled at a threat level of urgent by the CDC and as a high priority by WHO; both agencies have urged scientists and private sector drug developers to prioritize the identification and study of new, effective antibiotic treatment options for gonorrhea [CDC, 2019; CDC, 2015; WHO, 2017].

Gepotidacin is a first-in-class, novel triazaacenaphthylene antibacterial that has demonstrated in vitro activity against NG with gepotidacin MIC₉₀ values of 0.25 and 1 µg/mL for ciprofloxacin-susceptible and -nonsusceptible strains, respectively (see Section 4.2.1.3 in the investigator's brochure [IB]). In a Phase II study of uncomplicated urogenital gonorrhea caused by NG, microbiological success (bacterial eradication) was demonstrated for 97% and 95% of participants treated orally with single doses of 1500 and 3000 mg gepotidacin, respectively. With its unique ability to selectively inhibit bacterial DNA replication by a means not utilized by any currently approved human therapeutic agent, gepotidacin warrants further study in order to address an unmet medical need by providing a new and effective oral treatment option for gonorrhea.

A detailed description of the chemistry, pharmacology, efficacy, and safety of gepotidacin is provided in the IB. Details on the active comparator in this study, ceftriaxone plus azithromycin, may be found in locally approved prescribing information.

3.3. Benefit/Risk Assessment

More detailed information about the known and expected benefits and risks and reasonably expected adverse events (AEs) may be found in the IB for gepotidacin and in locally approved prescribing information for ceftriaxone and azithromycin.

3.3.1. Risk Assessment

Potential Risk of Clinical Significance	Summary of Data/Rationale for Risk	Mitigation Strategy
Gepotidacin (GSK2140944)		

Cardiovascular Effects
 
Based on nonclinical data, cardiovascular effects were reversible increase in heart rate and blood pressure (dog and monkey); reversible 10 to 21 msec (4% to 9%) increase in QTc (monkey); and at the highest dose, a reversible 2 to 3 msec (6% to 8%) increase in QRS (monkey).
 
Based on a thorough QTc clinical study, gepotidacin may cause mild, reversible heart rate effects and QT prolongation.
	
In a thorough QTc study, infusion of gepotidacin at doses of 1000 and 1800 mg over 2 hours caused a mild increased heart rate effect of approximately 6 to 10 bpm and QT prolongation measured as $\Delta\Delta\text{QTcF}$ of 12 to 22 msec. The QT prolongation evolved during the infusion and was quickly reversed over 2 hours after the end of the infusion (see Section 5.2.6 and Section 6 of the IB).
 
In Phase I and II studies, concentration-dependent QT prolongation has been observed during clinical trials with gepotidacin; however, this increase has not translated into medically significant QTc values or changes from baseline ($\text{QTcF} > 500$ msec or change from baseline > 60 msec) or cardiovascular safety concerns.
 
In Phase I and II studies, gepotidacin did not have a clinically relevant effect on cardiac conduction (PR and QRS intervals).
	
See Section 6.2 for excluded cardiac conditions. Close monitoring of clinical parameters and AEs (Section 2, Table 1) will be conducted, and treatment monitoring and evaluation criteria (Section 8.1.2) will be utilized to mitigate cardiovascular effects.
 
Participants taking medications known to increase QT or potent CYP3A4 inhibitors will be excluded (Section 7.7.2).
 
See also the Hepatic and Renal sections within this table below.

Potential Risk of Clinical Significance	Summary of Data/Rationale for Risk	Mitigation Strategy

Gastrointestinal Effects
 
Based on nonclinical data, gastrointestinal effects were mild ulceration of the nonglandular mucosa and minimal erosion and/or mural inflammation of the glandular mucosa in stomach (rat, oral study); moderate cecal ulceration and minimal colonic erosion (rat, IV study); and vomiting (dog).
 
Lower gastrointestinal effects (soft stools, flatulence, and diarrhea) are among the most common AEs reported in gepotidacin clinical studies. Nausea and vomiting AEs have also been commonly observed in gepotidacin clinical studies.
	
See also the Acetylcholinesterase Inhibition section within this table below.
 
Clostridium difficile-associated diarrhea has been observed in clinical trials with gepotidacin.
	
See Section 6.2 for excluded medical conditions. Close monitoring of clinical parameters and AEs (Section 2, Table 1) will be conducted to mitigate and assess gastrointestinal effects.
 
Suspected C. difficile infection will be managed according to a prespecified algorithm provided in Appendix 10.

Potential Risk of Clinical Significance	Summary of Data/Rationale for Risk	Mitigation Strategy

Acetylcholinesterase Inhibition
 
In vitro testing showed gepotidacin to be a rapidly reversible inhibitor of acetylcholinesterase in the clinical plasma concentration range.
 
Based on clinical data, caution should be used in participants who have a condition requiring treatment with anticholinergic medications or who have certain medical conditions that may be exacerbated by the acetylcholinesterase inhibition activity of gepotidacin.
	
Increased cholinergic effects can potentially be associated with more severe symptoms including atrioventricular block, seizure/convulsions, bronchospasm, and vasovagal syncope. No causal relationship between these events and the use of gepotidacin has been established during clinical trials to date.
 
Adverse events possibly consistent with acetylcholinesterase inhibition, including diarrhea, nausea, vomiting, gastrointestinal cramping and pain, dyspnea, bradycardia, lacrimation, salivation, dysarthria, and diaphoresis/sweating have been reported during clinical trials with gepotidacin.
 
The majority of these AEs have been mild and transient and have been reported in clinical trials with comparable C_{max} levels expected in this study.
	
Participants who have medical conditions or require medications that may be impacted by inhibition of acetylcholinesterase will be excluded from participation in this study. See Section 6.2, for excluded medical conditions and Section 7.7.2, Prohibited Medications and Nondrug Therapies, for prohibited medications.
 
Close monitoring of clinical parameters and AEs will be conducted to assess effects potentially related to acetylcholinesterase inhibition (Section 2, Table 1).

Potential Risk of Clinical Significance	Summary of Data/Rationale for Risk	Mitigation Strategy

Hepatic Effects
 
In preclinical studies, increases in ALT, GLDH, alkaline phosphatase, and total bilirubin were observed in some rat studies of varying exposure.
	
Elevations in ALT have occurred in a few participants with pre-existing hepatitis C infection, but none were felt related to study treatment. The type and pattern of elevation in liver transaminases observed has not been suggestive of an adverse effect of gepotidacin and none were considered related to study treatment.
 
A substantial increase in Cmax and AUC and decrease in clearance was observed in volunteer participants with severe hepatic impairment.
	
Participants with severe hepatic impairment are excluded from Phase III trials. See Section 6.2 for excluded medical conditions. Monitoring and stopping criteria liver events have been implemented.

Renal Effects
 
In preclinical trials, mild to moderate tubular degeneration was noted in the rat and proteinuria in the dog. Proteinuria was also observed in humans.
	
No clinical evidence of renal toxicity has been seen in clinical trials to date.
 
A substantial increase in Cmax and AUC and decrease in clearance was observed in severe renal impairment/ESRD participants not on hemodialysis and in ESRD participants requiring hemodialysis (note: gepotidacin may have been administered at any time other than when receiving dialysis).
	
Participants with severe renal impairment/ESRD (including those who may require dialysis) are excluded from Phase III trials. See Section 6.2 for excluded medical conditions. Monitoring criteria have been implemented.

Potential Risk of Clinical Significance	Summary of Data/Rationale for Risk	Mitigation Strategy

Reproductive System Effects
 
Preclinical studies demonstrated that gepotidacin was not genotoxic and no drug-related malformations were observed. Although positive in vitro findings for clastogenicity, consistent with a mechanism related to mammalian topoisomerase II inhibition were found, in vivo data from rat micronucleus and COMET assays suggest that gepotidacin does not pose a genotoxic hazard to humans.
 
Gepotidacin effects on embryofetal development were limited to decreased fetal weights for male and female fetuses in rats and decreased fetal weights and increased fetal resorptions (fetal deaths) in mice, both at maternally toxic doses. These occurred at clinically relevant exposures (65 µg.h/mL in rat and 35 µg.h/mL in mouse).
	
There are no data on the use of gepotidacin in pregnant women.
	
Gepotidacin is not recommended in pregnant or nursing mothers. Pregnancy testing requirements in this study minimize the risk of exposure to a fetus. See Appendix 6 for contraceptive measures and for required pregnancy testing.

Potential Risk of Clinical Significance	Summary of Data/Rationale for Risk	Mitigation Strategy
Other		

Ceftriaxone
	
Intramuscular administration of ceftriaxone may be associated with local injection site reactions, including pain, warmth or induration, or tenderness.
 
Some of the risks summarized for gepotidacin also apply to ceftriaxone, including the occurrence of gastrointestinal effects (diarrhea or loose stools) and the need to monitor for C. difficile-associated diarrhea. Other adverse effects include hepatic (AST and ALT elevations) and hematologic (eosinophilia, thrombocytosis, and leukopenia).
 
Additionally, ceftriaxone should not be reconstituted using diluents containing calcium, such as Ringer’s solution or Hartmann’s solution, because a precipitate can form.
 
Refer to the locally approved ceftriaxone prescribing information for specific details relating to ceftriaxone.
	
Close monitoring of clinical parameters and AEs (Section 2, Table 1) will be conducted, and treatment monitoring and evaluation criteria (Section 8.1.1) will be utilized to mitigate hepatic effects.
 
Participants with a history of sensitivity to ceftriaxone, or components thereof, will not be allowed to enroll in the study (Section 6.2). Participant’s medical history will be carefully evaluated for a history of hypersensitivity.
 
Suspected C. difficile infection will be managed according to a prespecified algorithm provided in Appendix 10.
 
Precautions related to ceftriaxone solution preparation are included in Section 7.5 and summarized in detail in the Study Reference Manual.

Potential Risk of Clinical Significance	Summary of Data/Rationale for Risk	Mitigation Strategy

Azithromycin
	
Some of the risks summarized for gepotidacin also apply to azithromycin, including the occurrence of gastrointestinal effects (diarrhea or loose stools) and the need to monitor for C. difficile-associated diarrhea and prolongation of the QT interval.
 
Azithromycin may also exacerbate muscle weakness in participants with myasthenia gravis. Other adverse effects include allergic and skin reactions and hepatotoxicity, which may be serious (including fatal).
	
Close monitoring of clinical parameters and AEs (Section 2, Table 1) will be conducted. Suspected C. difficile infection will be managed according to a prespecified algorithm provided in Appendix 10. See Section 6.2 for excluded cardiac conditions. Monitoring and evaluation criteria (Section 8.1.2) will be utilized to mitigate cardiovascular effects. In addition, participants taking QT-prolonging drugs or strong CYP3A4 inhibitors will be excluded. Participants with myasthenia gravis will be excluded.
 
Participants with a history of sensitivity to azithromycin, erythromycin, and any macrolide or ketolide drug will be excluded (Section 6.2). Participant’s medical history will be carefully evaluated for a history of hypersensitivity. Participants with a history of cholestatic jaundice or hepatic dysfunction associated with prior use of azithromycin will be excluded (Section 6.2). Treatment monitoring and evaluation criteria (Section 8.1.1) will be utilized to mitigate hepatic effects.

bpm=beats per minute; ABSSSI=acute bacterial skin and skin structure infection; AE=adverse event; ALT=alanine aminotransferase; AST=aspartate aminotransferase; AUC=area under the drug concentration-time curve; C_{max}=maximum concentration; CYP3A4=cytochrome P450 enzyme 3A4; ECG=electrocardiogram; ESRD=end-stage renal disease; GLDH=glutamate dehydrogenase; IC₅₀=inhibitory concentration inhibiting 50% of microbial isolates; IB=investigator’s brochure; IV=intravenous; ΔΔQTcF=placebo-corrected change from baseline in corrected QT interval using the Fridericia formula; QTc=corrected QT interval; QTcB=QT interval corrected for heart rate according to Bazett; QTcF=interval corrected for heart rate according to Fridericia.

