6. STUDY POPULATION

Prospective approval of protocol deviations to recruitment and enrollment criteria, also known as protocol waivers or exemptions, is not permitted.

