6.2. Exclusion Criteria

Participants are excluded from the study if any of the following criteria apply:

Medical Conditions and History

1. The participant is a male with a current diagnosis of epididymitis and/or orchitis at the time of the Baseline Visit.
2. The participant is suspected or confirmed to have a CT infection and per the investigator's judgement standard-of-care treatment for this infection cannot be safely postponed until the TOC Visit.
3. The participant has a body mass index ≥ 40 kg/m² or has a body mass index ≥ 35.0 kg/m² and is experiencing obesity-related health conditions such as uncontrolled high blood pressure or uncontrolled diabetes.
4. The participant has a history of sensitivity to the study treatments, or components thereof, or a history of a drug (including erythromycin and any macrolide or ketolide drug) or other allergy that, in the opinion of the investigator or medical monitor, contraindicates his or her participation.
5. The participant is immunocompromised or has altered immune defenses that may predispose the participant to a higher risk of treatment failure and/or complications (e.g., participants with uncontrolled diabetes, renal transplant recipients, participants with clinically significant persistent granulocytopenia [absolute neutrophil count $< 1000/\mu\text{L}$], and participants receiving immunosuppressive therapy, including corticosteroid therapy [> 40 mg/day prednisolone or equivalent for > 1 week, ≥ 20 mg/day prednisolone or equivalent for > 2 weeks, or prednisolone or equivalent

≥ 10 mg/day for >6 weeks]). Participants with a known CD4 count of <200 cells/mm³ should not be enrolled.

Note: Participants taking pre-exposure prophylactics for human immunodeficiency virus (HIV) are allowed to enroll. HIV-infected participants are allowed to enroll, as long as their CD4 count is ≥ 200 cells/mm³. Use of strong cytochrome P450 enzyme 3A4 (CYP3A4) inhibitors during the study is prohibited (see Exclusion Criterion 15).

6. The participant has any of the following:
 - Medical condition that requires medication that may be impacted by inhibition of acetylcholinesterase, such as:
 - Poorly controlled asthma or chronic obstructive pulmonary disease at the Baseline Visit and, in the opinion of the investigator, not stable on current therapy
 - Acute severe pain, uncontrolled with conventional medical management
 - Active peptic ulcer disease
 - Parkinson disease
 - Myasthenia gravis

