 - A history of seizure disorder requiring medications for control (this does not include a history of childhood febrile seizures)

OR

- Any surgical or medical condition (active or chronic) that may interfere with drug absorption, distribution, metabolism, or excretion of the study treatment (e.g., ileostomy or malabsorption syndrome).
7. The participant has known anuria, oliguria, or severe impairment of renal function (creatinine clearance <30 mL/min or clinically significant elevated serum creatinine as determined by the investigator).
 8. The participant, in the judgment of the investigator, would not be able or willing to comply with the protocol or complete study follow-up.
 9. The participant has a serious underlying disease that could be imminently life threatening, or the participant is unlikely to survive for the duration of the study period.

Cardiac Exclusions

10. The participant has congenital long QT syndrome or known prolongation of QTc.
11. The participant has uncompensated heart failure.
12. The participant has severe left ventricular hypertrophy.
13. The participant has a family history of QT prolongation or sudden death.
14. The participant has a recent history of vasovagal syncope or episodes of symptomatic bradycardia or bradyarrhythmia within the last 12 months.

15. The participant is taking QT-prolonging drugs or drugs known to increase the risk of torsades de pointes (TdP) per the www.crediblemeds.org “Known Risk of TdP” category at the time of his or her Baseline Visit, which cannot be safely discontinued from the Baseline Visit to the TOC Visit; or the participant is taking a strong CYP3A4 inhibitor.

Cardiac ECG Exclusions

16. For any participant ≥ 12 to < 18 years, the participant has an abnormal ECG reading.
17. The participant has a QTc > 450 msec or a QTc > 480 msec for participants with bundle-branch block.

Note:

- The QTc is the QT interval corrected for heart rate according to either Bazett’s formula (QTcB), or Fridericia’s (QTcF) formula, and/or another method. It is either machine read or manually overread.
 - The specific formula used to determine eligibility and discontinuation for an individual participant should be determined prior to initiation of the study. In other words, several different formulas cannot be used to calculate the QTc for an individual participant and then the lowest QTc value used to include or discontinue the participant from the trial.

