7.3. Method of Treatment Assignment

Participants will be stratified by sex and sexual orientation combination (MSM, MSW, or females) and age (<18 years, ≥18 to 65 years, or >65 years) to ensure that treatment groups are balanced within each category. The MSM category will include MSM and bisexual males (i.e., male participants who have sex with both males and females). Within each stratum, participants will be centrally randomized in a 1:1 ratio to either gepotidacin or ceftriaxone plus azithromycin using an interactive response technology (IRT) in accordance with the randomization schedule generated by or under the direction of GSK's Clinical Statistics. Before the study is initiated, information and directions for the IRT will be provided to each study site.

Each participant scheduled to receive study treatment will receive a randomization number at the time of randomization. This randomization number will be used to identify the participant and indicate the treatment to be administered to that participant.

For those participants randomly assigned to gepotidacin, the first dose will be administered at the study site during the Baseline Visit and the second dose will be dispensed to participants during this visit for self-administration 10 to 12 hours after the

first dose (see Section 7.1). Participants randomly assigned to ceftriaxone plus azithromycin will be administered a single IM dose of ceftriaxone plus a single oral dose of azithromycin during the Baseline Visit.

Returned gepotidacin should not be re-dispensed to other participants.

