7.6. Treatment Compliance

- When the individual dose for a participant is prepared from a bulk supply, the preparation of the dose will be confirmed by a second member of the study site staff.
- Participants dosed at the study site will receive study treatment (oral dose of gepotidacin or single IM dose of ceftriaxone plus an oral dose of azithromycin) directly from the investigator or designee, under medical supervision. The date and time of each dose administered in the study site will be recorded in the source documents and reported in the eCRF. The dose of study treatment and study participant identification will be confirmed at the time of dosing by a member of the study site staff other than the person administering the study treatment.
- Participants will self-administer the second oral dose of gepotidacin as an outpatient (see Section 7.1). Compliance with gepotidacin will be assessed by contacting the participant via telephone, email, or text message. The participants should confirm that the second dose was taken. Study site staff will also query the participant during the TOC Visit and document whether the second dose was taken. A record of the number of gepotidacin tablets dispensed to each participant must be recorded and reconciled with study treatment and compliance records. The date and time of each dose will also be recorded in the eCRF.

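### Section 3.3.1 states an outright exclusion for erythromycin, macrolide or ketolide sensitivity, but exclusion criterion 4 leaves it to clinician opinion

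*Protocol*

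**What the plan says.** Protocol Section 3.3.1, azithromycin row, mitigation column: "Participants with a history of sensitivity to azithromycin, erythromycin, and any macrolide or ketolide drug will be excluded (Section 6.2"). The sentence carries no condition and gives Section 6.2 as its source. The sentence after it adds that the participant's "medical history will be carefully evaluated for a history of hypersensitivity".

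Protocol Section 6.2, exclusion criterion 4, has two parts. The first is a history of sensitivity to the study treatments or their components. The second reads in part: "a history of a drug (including erythromycin and any macrolide or ketolide drug) or other allergy that, in the opinion of the investigator". The rest of that clause lets the medical monitor give the opinion too, and makes the allergy count only if it is thought to rule out entry. Erythromycin, macrolides and ketolides are named in the second part.

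Protocol Section 6 opens by closing off exceptions: "Prospective approval of protocol deviations to recruitment and enrollment criteria, also known as protocol waivers or exemptions, is not permitted".

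**The concern.** The two texts give different answers for the same person. Take someone with a past reaction to erythromycin or clarithromycin-type drugs, no known azithromycin reaction, and an investigator who thinks entry is acceptable. Section 3.3.1 says this person is excluded. Criterion 4 says this person may enter and be randomised to a regimen that contains azithromycin 1 g.

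What is at stake is a stated safety measure. Section 3.3.1 lists allergic and skin reactions among azithromycin's possibly serious effects and offers this exclusion as a mitigation. The benefit-risk conclusion in Section 3.3.3 relies on the mitigations in 3.3.1. An ethics committee reading that table is told of a categorical exclusion that sites are not bound to apply. Two sites could decide differently about the same patient and both comply with Section 6.2.

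**Working it through.** This is a comparison of texts. The plan has no figure to reproduce.

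**1. The two rules side by side**

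| History of sensitivity or allergy to | Section 3.3.1 | Section 6.2, criterion 4 |
|---|---|---|
| Azithromycin | Excluded | Excluded (it is a study treatment) |
| Erythromycin | Excluded | Excluded only if judged to contraindicate entry |
| Any other macrolide, or a ketolide | Excluded | Excluded only if judged to contraindicate entry |

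**2. How far the opinion clause reaches.** In criterion 4, the words before and after the parenthesis form a single phrase covering drug allergy and other allergy, and the opinion clause qualifies the whole of it. If the clause were tied only to the other allergies, every drug allergy of any kind would be an outright exclusion, which is not a plausible intention. If the clause were stretched back over the study-treatment part, azithromycin sensitivity would become discretionary too and the mismatch would be wider.

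**3. Whether another rule closes the gap.** Criterion 19 concerns azithromycin but covers only cholestatic jaundice or hepatic dysfunction with prior use. None of the remaining criteria in Section 6.2 deals with macrolide or ketolide allergy, and neither does the prohibited-medication list in Section 7.7.2.

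**4. Size.** Protocol Section 7.3 states that "participants will be centrally randomized in a 1:1 ratio to either gepotidacin or ceftriaxone plus azithromycin". Let k be the number of people with such an allergy who are admitted on clinician judgement.

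- Chance that an admitted person is allocated azithromycin: 1/(1 + 1) = 0.50.
- Expected number given azithromycin 1 g: 0.50 × k.
- The documents do not give k. As an assumption, k = 0, 1 and 4 give 0, 0.5 and 2.

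This only restates the allocation ratio. No cross-reaction risk is given, so no number of reactions can be derived.

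**5. Statistical consequences.** None of the inputs to the sample size, the power table or the primary analysis depends on this criterion.

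**The case against.** The strongest reply is that Section 3.3.1 is a risk summary, not an eligibility rule. Its sentence points to Section 6.2, and a site screening a patient has one rule to apply. Section 3.3.1 also shortens other criteria. The same azithromycin cell says that participants taking QT-prolonging drugs will be excluded, while criterion 15 limits this to drugs "which cannot be safely discontinued from the Baseline Visit to the TOC Visit; or the participant is taking a strong CYP3A4 inhibitor". The acetylcholinesterase row speaks generally of affected medical conditions, while criterion 6 covers "Poorly controlled asthma or chronic obstructive pulmonary disease at the Baseline Visit and, in the opinion of the investigator, not stable on current therapy". On this view the wording is summary style and the matter is editorial.

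The practical safeguards are also real. Azithromycin sensitivity is already excluded. Criterion 4 names the drug classes, so sites are prompted to ask. A clinician must judge the history. Azithromycin is given on site "directly from the investigator or designee, under medical supervision".

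Most of this stands as a limit on severity. It does not remove the mismatch. That Section 6.2 alone governs eligibility is exactly why the exclusion described in 3.3.1 is not in force. The azithromycin sentence is also more than loose shorthand: it names the same additional drugs that criterion 4 names and omits the condition attached to them. A pattern of abbreviation explains how the sentence arose but does not make it accurate.

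**Conclusion.** The concern holds as a minor inconsistency. The exclusion stated in Section 3.3.1 is stricter than criterion 4 for erythromycin, other macrolides and ketolides. For azithromycin itself the two agree on the natural reading.

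The number of people affected is unknown and may be zero. Half of any who are admitted would be expected to receive azithromycin. No raised risk is claimed, because the documents give no cross-reaction rate. The conclusion rests on reading the opinion clause in criterion 4 as covering all drug allergy in its second part, which is the only reading that makes sense of the sentence.

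**What to change.** Preferred: reword criterion 4 so that judgement applies only to other allergies. The unconditional part would list sensitivity to the study treatments or their components, to erythromycin, or to any macrolide or ketolide. The discretionary part would cover any other drug or non-drug allergy that the investigator or medical monitor considers a contraindication. Section 3.3.1 then stands as written.

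Alternative: if clinician judgement is the intended rule, add the same qualifier to the Section 3.3.1 sentence. This aligns the two texts but changes no one's eligibility.

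Either is a one-sentence protocol amendment. The rewording acts only on participants screened after it takes effect. Its cost is possibly a few more screen failures among people whom an investigator would have accepted. Because it adopts the term *sensitivity* from Section 3.3.1 where the second part of criterion 4 speaks of allergy, it may also catch some non-allergic intolerance. The sponsor should confirm that this is wanted.
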